10.2.9.4 Reporting of Liver Function Test Abnormalities

If a subject is noted to have ALT or AST $>3 \times$ ULN and total bilirubin $>2 \times$ ULN for which an alternative etiology has not been identified, the event should be recorded as an SAE and reported as per Section 10.2.9.3. The investigator or sub-investigator will contact the study monitor and investigate the subject details and possible alternative etiologies (eg, acute viral hepatitis A or B, other acute liver disease). Follow-up tests described in Section 9.2.9 will also be performed.

10.2.10 Safety Reporting to Investigators, IRBs, and Regulatory Authorities

The sponsor will be responsible for reporting all serious unexpected suspected adverse reactions (SUSARs) and any other SAEs for expedited reporting to the regulatory authorities, investigators, and IRBs. Relative to the first awareness of the event by/or further provision to the sponsor or sponsor's designee, SUSARs

will be submitted to the regulatory authorities as expedited reports within 7 days for fatal and life-threatening events and 15 days for other serious events, unless otherwise required by national regulations. The sponsor will also perform expedited reporting of other significant safety information that may greatly affect the current benefit-risk profile of the study drug or require a change to the study treatment or overall conduct of the study. The study site also will forward a copy of all expedited reports to the IRB.

11.0 STATISTICAL METHODS

11.1 Statistical and Analytical Plans

A statistical analysis plan (SAP) will be prepared and finalized prior to database lock. This document will provide further details regarding the definition of analysis sets, analysis variables and analysis methodology to address all study objectives.

Analysis will be performed after database lock using the data obtained so far. Also, when an additional study is performed, another analysis will be performed using combined data of the first study with data of the additional study.

11.1.1 Analysis Sets

In this study, two kinds of analysis sets are defined: pharmacokinetics analysis set and safety analysis set.

The sponsor will verify the validity of the definitions of the analysis sets as well as the rules for handling data prior to database lock.

11.1.1.1 Safety Analysis Set

The “safety analysis set” will be defined as all the subjects who received at least one dose of the study drug.

11.1.1.2 Pharmacokinetics Analysis Set

The “pharmacokinetics analysis set” is a subset of all treated subjects who had no major protocol violations, have completed the minimum element of the protocol, and had evaluable pharmacokinetic data.

11.1.2 Analysis of Demographic and Other Baseline Characteristics

Demographic and other baseline characteristics will be summarized using the pharmacokinetic analysis set and the safety analysis set.

11.1.3 Pharmacokinetic Analysis

1. Endpoints and their analytical method

[Endpoint]

Primary endpoints

- AUC_{last} of Lu AA21004
- C_{max} of Lu AA21004

Secondary endpoints

- AUC_{∞} , t_{max} , MRT, λ_z and $t_{1/2z}$ of Lu AA21004

[Analytical method]

The following analyses will be based on the pharmacokinetic analysis set.

1) Plasma concentration and pharmacokinetic parameters

The descriptive statistics for plasma concentration of Lu AA21004 will be provided for each formulation (Lu AA21004 20 mg tablet and 10 mg tablet) by visit and the mean and standard deviation of plasma

concentration will be plotted for both formulations on the same graph. The descriptive statistics for PK parameter will be provided for each formulation.

2) Bioequivalence assessment

The bioequivalence of Lu AA21004 20 mg tablet and 2× 10 mg tablets is evaluated.

The log-transformed (natural log) PK parameters AUC_{last} and C_{max} of Lu AA21004 will be analysed separately using analysis of variance (ANOVA) with dosing formulation, treatment sequence, administration period as fixed effects and the two-sided 90% confidence interval (CIs) for the differences between the formulations and between the periods will be provided. The log-transformed (natural log) PK parameters AUC_{∞} , MRT, λ_z and $t_{1/2z}$ of Lu AA21004 and t_{max} of Lu AA21004 will be analysed separately using ANOVA in the same manner (confidence coefficient 90%, 95%).

Bioequivalence for Lu AA21004 will be assessed based on "Guideline for Bioequivalence Studies of Generic Products". Formulations are considered to be bioequivalent if any of the following criteria are met.

If bioequivalence cannot be verified, it will be considered adding additional subjects.

- For the primary endpoints (AUC_{last} and C_{max}), the two-sided 90% CIs of the difference in the mean values of logarithmic parameters to be assessed between two treatments is within the acceptable range of $\ln(0.80)$ to $\ln(1.25)$.

3) Methods of data transformation and handling of missing data

For plasma concentrations, values below the lower limit of quantification will be treated as Zero. Subjects with any missing pharmacokinetic data for some reasons (e.g., discontinuation, inadequate measurement) will be excluded from the pharmacokinetic analysis set, however, the PK parameters, such as $t_{1/2z}$, will be calculated, as far as possible.

4) Significance level and confidence coefficient

- Significance level: 5% (one-sided test)
- Confidence coefficient : 90% (two-sided)
: 95% (two-sided)

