11.2 Determination of Sample Size

Planned number of subjects is 28 (14 per treatment sequence).

The planned sample size was calculated based upon the analysis of logarithmically transformed AUC_{last} and C_{max} . If the 90% CIs for the ratios of Lu AA21004 20 mg tablets and $2 \times$ Lu AA21004 10 mg tablets ($2 \times$ Lu AA21004 10 mg tablets/ Lu AA21004 20 mg tablet) geometric mean value of AUC_{last} and C_{max} are both be within the limits of 80.00% to 125.00%, bioequivalence can be verified. It is hypothesize that there is no interaction between dosing formulation and administration period at AUC_{last} and C_{max} . Based on data from previous studies, the largest estimate of the within-subject coefficient of variation (CV) of AUC_{last} and C_{max} were up to 9.5% and 14.3% and a sample size of 24 would then provide a power of 99.8% and 91.5% for each correctly concluding bioequivalence even if the true ratio is 1.1. Given that the 90% CIs for the ratio of the geometric means for AUC_{last} and C_{max} must both be contained in 80.00% to 125.00% in order to conclude bioequivalence between the two treatments, 24 subjects provided an overall power of at least 91.3%, assuming that the two endpoints AUC_{last} and C_{max} are independent.

Taking into account possible occurrence of dropouts, planned number of subjects is 28.

In case bioequivalence cannot be demonstrated with the number of subjects initially planned due to the insufficiency of the number of subjects, an add-on subject study will be conducted in accordance with the Partial Revision of Guideline for Bioequivalence Studies of Generic Products, if applicable. The maximum number of additional subjects in the add-on subject study is 28 (14 per treatment sequence), which is determined based on study feasibility, but is not on statistical consideration.

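### Does the any-of wording in Section 11.1.3 allow bioequivalence to be declared on AUClast or Cmax alone?

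*Protocol*

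**What the plan says.** Section 11.1.3, under the bioequivalence assessment, states: "Formulations are considered to be bioequivalent if any of the following criteria are met". A sentence on considering additional subjects comes next, and then a single bullet. That bullet begins "For the primary endpoints (AUC_{last} and C_{max}), the two-sided 90% CIs of the difference in the mean values of logarithmic parameters" and requires these to lie between ln(0.80) and ln(1.25). The same section fixes "Significance level: 5% (one-sided test"), which corresponds to the two-sided 90% interval.

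Section 11.2 treats success as joint. It first says bioequivalence can be verified if the intervals for both parameters are inside 80.00% to 125.00%. It then says that they "must both be contained in 80.00% to 125.00% in order to conclude bioequivalence between the two treatments", and derives an overall power of at least 91.3% on that footing. The sample-size rationale in the study summary (Section 1.0) repeats both statements.

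**The concern.** Section 11.1.3 is where an analyst looks for the primary decision rule, and its lead-in is disjunctive. The bullet beneath it covers two endpoints, pairs a plural subject with a singular verb and never uses the word both. The two parameters are also analysed separately, each with its own interval. A reader could therefore split the bullet and let either endpoint carry the conclusion, or could suspect that alternative criteria were meant to be listed and were left out.

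On the split reading, a pass on AUClast would override a failure on Cmax. Section 4.2 gives a difference in dissolution between the two strengths as the reason for the study, so a result in which extent matches and rate does not is conceivable. The same rule also decides whether additional subjects are considered.

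**Working it through.** **Wording, side by side**

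| Place | Endpoints | How they are joined |
|---|---|---|
| Section 11.1.3, lead-in | none named | any of a list |
| Section 11.1.3, the only bullet | AUClast and Cmax | one criterion, with intervals in the plural |
| Section 11.2, two statements | AUClast and Cmax | both |
| Section 1.0, two statements | AUClast and Cmax | both |

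Any item of a one-item list is that item, and that item is joint. No sentence in the protocol says that one endpoint is enough.

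**Which rule the stated power belongs to**

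Inputs from Section 11.2: within-subject CV 9.5% (AUClast) and 14.3% (Cmax), 24 subjects, limits 0.80 to 1.25, and power claimed "even if the true ratio is 1.1". From Section 11.1.3: one-sided 5%. The design is a 2×2 crossover, so there are 24 − 2 = 22 degrees of freedom.

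1. Within-subject SD on the log scale is sqrt(ln(1 + CV²)). AUClast: sqrt(ln(1.009025)) = 0.0948. Cmax: sqrt(ln(1.020449)) = 0.1423.
2. The standard error of the formulation difference is SD × sqrt(2/24). AUClast: 0.0948 × 0.2887 = 0.0274. Cmax: 0.1423 × 0.2887 = 0.0411.
3. The distance from the true difference to the nearer limit is ln(1.25) − ln(1.1) = 0.2231 − 0.0953 = 0.1278.
4. Exact power of the two one-sided tests, integrating over the distribution of the residual variance: AUClast 99.80%, Cmax 91.46%. The protocol states 99.8% and 91.5%, so both reproduce.
5. Both must pass, endpoints independent: 0.9980 × 0.9146 = 0.9128, the stated 91.3%.
6. Either suffices, endpoints independent: 1 − (1 − 0.99799)(1 − 0.91461) = 1 − 0.00201 × 0.08539 = 0.9998.

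The protocol's figure is the one in step 5.

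**What an either-endpoint rule would cost (n = 24, protocol CVs)**

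| True AUClast ratio | True Cmax ratio | Both must pass | Either suffices |
|---|---|---|---|
| 1.1 | 1.1 | 91.3% | 99.98% |
| 1.1 | 1.25 | 5.0% | 99.8% |
| 1.00 | 1.25 | 5.0% | about 100% |
| 1.00 | 1.30 | 0.5% | about 100% |

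With both true ratios at 1.25 and independent endpoints, false acceptance under the either rule is 1 − 0.95² = 9.75%. Under the both rule it cannot exceed 5%, whatever the correlation, because concluding bioequivalence requires each 5% test to reject.

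Only the first row uses the protocol's planning ratio for both endpoints. The others are illustrative true ratios, and the right-hand column prices a rule that the protocol does not contain.

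**The case for a change.** The best argument for a change is that a primary success criterion should have one reading before data are seen, and that the correction would take one sentence. The any-of phrase is wrong on its face when one criterion follows. The sentence on additional subjects separates the rule from its bullet. If AUClast passed and Cmax failed, a reader holding only Section 11.1.3 might ask whether the trial had succeeded or whether more subjects should be considered.

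The criticism of the drafting stands: the lead-in is loose, and aligning it with Section 11.2 would do no harm if the protocol were being amended for another reason. The rest does not carry. The singular verb is weak evidence of intent, since the text has similar slips elsewhere, including inside Section 11.2's own both-endpoints sentence. A plural lead-in does not show that an alternative criterion existed and was omitted; none is listed. Section 4.2 reports different dissolution behaviour but does not say that a Cmax difference is the expected failure. A split result is already settled by Sections 1.0 and 11.2, which phrase the both-endpoint requirement as a condition for concluding bioequivalence and not merely as a power assumption: bioequivalence is not shown, and the provision for additional subjects comes into play.

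**Conclusion.** No change to the plan is needed. The any-of phrase is a clerical slip ahead of a single joint criterion, and an analyst following the protocol will require both 90% intervals to lie within the limits. Under that reading power is 91.3% at 24 subjects and 94.8% if all 28 are evaluable (99.95% × 94.82%), with type I error at most 5%. Rewording would move none of these figures. The power figures assume the protocol's CVs, a true ratio of 1.1 for both parameters and independent endpoints; the 5% bound does not need independence. The conclusion rests on reading the one bullet as a whole and alongside Sections 1.0 and 11.2. It would change only if another governing document set out an either-endpoint rule, and nothing in this protocol does so.

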6.2.3 Rationale for Washout Period

In CPH-004 study (‘A Phase 1, Open-Label, Single-Dose, 2-Period Crossover Study to Assess Pharmacokinetics of Lu AA21004 and Effect of Food on the Pharmacokinetics after Oral Administration of Lu AA21004 in Healthy Male Subjects’), in which 14 days interval between the Period 1 dosing and the Period 2 dosing of the study drug, plasma unchanged Lu AA21004 concentration at Period 2 predose was

higher than 11% of C_{max} value of the Period 1 in the subject with the highest plasma unchanged Lu AA21004 level in Period 1. Based on these results, it is set that the interval between the Period 1 dosing and the Period 2 dosing of the study drug will be at least 3 weeks in order for the plasma concentration at Period 2 predose to be decreased below 5% of C_{max} in Period 1. Also, the Partial Revision of Guideline for Bioequivalence Studies of Generic Products recommends that there should be a washout period at least 5 times longer than the apparent half-life of the investigational drug. The 3 weeks interval between the Period 1 dosing and the Period 2 dosing of the study drug in this study is longer than 5 times of the apparent elimination half-life of Lu AA21004 (about 66 hours) thus meets this guideline.

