7.2 Exclusion Criteria

The subject meeting any of the following criteria will be excluded from the study:

1. Has received any investigational drugs within 90 days before screening for this study.
2. Previously received Lu AA21004 before participation in this study.
3. Is an employee of the sponsor or the study site, or immediate family member, or is in a dependent relationship with a study site employee who is involved in the conduct of this study (eg, spouse, parent, child, sibling) or who may be coerced to provide consent.

4. Has uncontrolled, clinically relevant neurologic, cardiovascular, pulmonary, hepatic, renal, metabolic, gastrointestinal, or endocrine disease or other abnormality which may affect study participation or study results.
5. Has a history of multiple episodes or severe allergies (eg, food, drug, latex allergy) or has had an anaphylactic reaction or significant intolerance to prescription drugs, OTC drugs, or foods.
6. Has a positive pregnancy test at the time of screening or Day –1.
7. Is a pregnant or lactating female.
8. Has a positive urine drug test at the time of screening or Day –1.
9. Has a history of drug abuse (defined as any illicit drug use) or has a history of alcohol dependence within 2 years before the start of screening or is unwilling to agree to abstain from alcohol and drugs throughout the study.
10. Consumes 6 or more servings of caffeinated beverages (containing about 720 mg of caffeine or more) such as coffee, tea, cola, or energy drinks per day .
11. Is a smoker who smoked cigarettes or used nicotine-containing products (such as nicotine patch) within 6 months before the Period 1 study drug administration.
12. Used any of the excluded drugs, dietary products or foods during the period specified in the table in Section 7.3, or will need any of them during the study period.
13. Has any current or a history of gastrointestinal diseases that would be expected to influence the absorption of drugs (ie, malabsorption, esophageal reflux, peptic ulcer disease, erosive esophagitis, frequent [more than once per week] occurrence of heartburn), or any surgical intervention (gastrectomy, cholecystectomy etc.).
14. Has a history of cancer.
15. Has a positive test result for any of the following at the time of screening: hepatitis B surface antigen (HBsAg), hepatitis C virus (HCV) antibody, human immunodeficiency virus (HIV) antibody/antigen, serological test for syphilis.
16. Has poor peripheral venous access.

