9.3.1 Pharmacokinetic Measurements

The pharmacokinetic parameters will be calculated from plasma concentrations of unchanged Lu AA21004 in the pharmacokinetic analysis set.

Term	Definition
AUC_{last}	Area under the plasma concentration-time curve from time 0 to time of the last quantifiable concentration Calculation Formula: Time 0 is taken as t_1 , and the last time point when the concentration exceeding the lower limit of quantification (C_{last}) is taken as $t_n (= t_{last})$ $AUC_{last} = \sum_{i=2}^n \frac{(C_i + C_{i-1})}{2} (t_i - t_{i-1})$
AUC_{∞}	Area under the plasma concentration-time curve from time 0 to infinity Calculation Formula: $AUC_{\infty} = AUC_{last} + C_{last} / \lambda_z$
C_{max}	Maximum plasma concentration (Observed value)
t_{max}	Time to reach C_{max} (Observed value)
$t_{1/2z}$	Apparent elimination half-life
$MRT_{\infty, ev}$	Mean residence time Calculation Formula: $MRT_{\infty, ev} = AUMC_{\infty} / AUC_{\infty}$
$MRT_{last, ev}$	The average residence time from 0 hour to time of the last quantifiable concentration Calculation Formula: $MRT_{last, ev} = AUMC_{last} / AUC_{last}$
λ_z	Apparent elimination rate constant
$AUMC_{\infty}$	Area under the first moment time curve from 0 hour to infinity Calculation Formula: $AUMC_{\infty} = AUMC_{last} + C_{last} \times t_{last} / \lambda_z + C_{last} / \lambda_z^2$
$AUMC_{last}$	Area under the first moment time curve from 0 hour to final determinable (By the trapezoidal method)

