9.3.1.1 Pharmacokinetic Samples

The blood samples for pharmacokinetic analysis of unchanged Lu AA21004 will be collected according to [Table 9.c](#).

The time of each sample collection will be recorded in the source documents and eCRF.

Table 9.c Collection of Pharmacokinetic Samples (in Both Period 1 and Period 2)

Analyte	Matrix	Time points of sample collection
Unchanged Lu AA21004	Plasma	Predose, 1, 2, 4, 6, 8, 10, 12, 14, 16, 24, 36, 48 and 72 hours postdose

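### As worded, one missing PK value among 28 samples removes a subject from both primary analyses, even when AUClast and Cmax can be derived in both periods: a minor loss of precision that is cheap to avoid

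*Protocol*

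**What the plan says.** Protocol 11.1.3 bases all pharmacokinetic analyses, including both primary ANOVAs, on the pharmacokinetic analysis set. Item 3 of that section sets the rule for missing data: "Subjects with any missing pharmacokinetic data for some reasons (e.g., discontinuation, inadequate measurement) will be excluded from the pharmacokinetic analysis set". The sentence then adds that parameters such as the terminal half-life "will be calculated, as far as possible".

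Two other sections bear on the same set. Section 11.1.1.2 admits treated subjects without major violations who "have completed the minimum element of the protocol, and had evaluable pharmacokinetic data"; neither the minimum element nor evaluability is defined. Section 9.3.1 says: "The pharmacokinetic parameters will be calculated from plasma concentrations of unchanged Lu AA21004 in the pharmacokinetic analysis set".

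Table 9.c lists the sampling times for each period: "Predose, 1, 2, 4, 6, 8, 10, 12, 14, 16, 24, 36, 48 and 72 hours postdose". That is 14 samples per period and 28 per subject.

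On numbers, 11.2 bases power on 24 subjects and then states: "Taking into account possible occurrence of dropouts, planned number of subjects is 28".

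**The concern.** The rule has no threshold. It lists inadequate measurement beside discontinuation, so it reaches a subject who completed both periods and lost one tube or one assay. Such a subject may still have AUClast and Cmax in both periods, which is all the primary analyses need. The second half of the sentence confirms that the rule foresees excluded subjects whose parameters can be derived.

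The phrase could instead mean missing parameters rather than missing samples. That reading is no better: a subject lacking only a secondary parameter, such as the terminal half-life, would then leave both primary analyses.

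What is at stake is usable within-subject data. The four subjects above 24 are described as cover for dropouts, and completers with one lost value would draw on the same four. If the first stage then failed for lack of numbers, the remedy in 11.2 is an add-on study of up to 28 further subjects. More healthy volunteers would be dosed partly to replace data already in hand.

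**Working it through.** **Inputs.** From 11.2: within-subject CV 9.5% (AUClast) and 14.3% (Cmax), true ratio 1.1, limits 0.80 to 1.25, N = 24 for power, 28 planned (14 per sequence). From 11.1.3: one-sided 5%, that is, a 90% confidence interval. From Table 9.c: 28 samples per subject. The per-sample loss rate q is an assumption, because the protocol gives none.

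**Step 1: reproduce the plan's figure.** The power of two one-sided tests in a 2×2 crossover uses s = √ln(1+CV²), SE = s·√(½(1/n₁+1/n₂)) and N−2 degrees of freedom. Joint power is the product of the two endpoint powers (independence, as in 11.2). At N = 24:

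- AUClast 99.80%, Cmax 91.46%, joint 0.9980 × 0.9146 = 91.28%.
- Stated: 99.8%, 91.5% and at least 91.3%. These agree.

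**Step 2: joint power by number of subjects kept.**

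| N (split) | Ratio 1.1 | Ratio 1.05 |
|---|---|---|
| 28 (14/14) | 94.8% | 99.8% |
| 24 (12/12) | 91.3% | 99.3% |
| 23 (12/11) | 90.05% | 99.1% |
| 23 (14/9) | 88.75% | 98.9% |

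**Step 3: exclusions under the rule as written.** With independent losses, P(subject excluded) = 1 − (1−q)²⁸. For clustered losses, a beta-binomial with an assumed within-subject correlation of 0.1 replaces this. Mean power sums the joint power over binomial numbers kept in each sequence of 14, with no other dropouts.

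| Assumed q | Losses | P(excluded) | Expected exclusions of 28 | P(fewer than 24 left) | Mean joint power, ratio 1.1 |
|---|---|---|---|---|---|
| 0.1% | independent | 2.8% | 0.8 | 0.1% | 94.2% |
| 0.25% | independent | 6.8% | 1.9 | 3.8% | 93.2% |
| 0.5% | independent | 13.1% | 3.7 | 30% | 91.3% |
| 1% | independent | 24.5% | 6.9 | 85% | 86.5% |
| 0.1% | clustered | 1.3% | 0.4 | <0.1% | 94.5% |
| 0.25% | clustered | 3.2% | 0.9 | 0.2% | 94.1% |
| 0.5% | clustered | 6.4% | 1.8 | 3.0% | 93.3% |
| 1% | clustered | 12.3% | 3.5 | 26% | 91.5% |

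At ratio 1.05 the lowest mean in these scenarios is 98.2% (q = 1%, independent).

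**Step 4: the most that can be gained.** A derivability rule can at best restore 94.8%. The gain at ratio 1.1 is therefore at most 0.6, 1.6, 3.5 or 8.3 points with independent losses (94.8 minus 94.2, 93.2, 91.3, 86.5) and 0.3, 0.7, 1.5 or 3.3 points with clustered losses. The four spare subjects are used up on average when 28·(1−q)²⁸ = 24, which gives q = 1 − (24/28)^(1/28) = 0.55%, about one tube in 180.

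**Step 5: which losses matter for AUClast.** This uses an illustrative one-compartment curve (an assumption: half-life 66 h and tmax 7 to 11 h, the values in 4.1) on the Table 9.c grid. One isolated loss from 1 to 48 h, bridged by the linear trapezoid, changes AUClast by at most 0.35%. Loss of the 72 h sample changes it by −26% to −27%.

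**The case against.** The strongest reply is that item 3 simply gives content to the general term in 11.1.1.2, that 11.1 leaves further detail on analysis sets to the SAP, and that 11.1.1 has the sponsor verify the definitions before database lock. A prespecified complete-data rule also leaves little discretion in an open-label study. Part of this stands. The two sections are in tension rather than plainly contradictory, because evaluability is undefined. A reader might infer that 9.3.1 contradicts the exclusion, but calculating parameters within a set does not conflict with removing subjects from it; only the closing clause of item 3 sits awkwardly with 9.3.1. The SAP does not settle the point, because item 3 is a stated rule and not an omission: a SAP that softened it would depart from the protocol.

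The second reply concerns size, and most of it stands. All samples fall within inpatient stays, 6.2.5 gives PK draws priority over other scheduled procedures, and Appendix C sets windows of 5 to 10 minutes. Low loss rates are therefore likely. With clustered losses, mean power does not fall below the planned 91.3% in any scenario shown, and 11.2 itself treats ratio 1.1 as an unfavourable case. Section 7.9 also allows a new subject to be enrolled for one who discontinues after dosing, so dropouts need not consume the four spares. On its wording, however, 7.9 does not cover a completer with a lost sample.

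**Conclusion.** The point holds as a minor, cheap improvement. Read as written, 11.1.3 item 3 discards subjects whose primary parameters are available in both periods.

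The size is conditional on an assumed loss rate. At ratio 1.1 the loss of mean joint power is at most 1.6 points for per-sample losses up to 0.25%. It reaches 8.3 points only if 1% of samples (about 8 of 28 × 28 = 784) are lost independently. The figures assume the CVs in 11.2, independent endpoints and no other dropouts.

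A reader might infer that the trial is underpowered or the sample size miscalculated. The documents do not support that: the stated power reproduces, and 24 subjects split evenly still give 91.3%. Nor do they give grounds for alleging bias or an inflated type I error.

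**What to change.** Replace the exclusion sentence in 11.1.3 item 3 with wording such as: *A subject is included in the analysis of each primary parameter (AUClast, Cmax) that can be derived in both periods; missing secondary parameters or isolated missing samples do not by themselves exclude a subject.*

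Fix the criteria for a non-derivable parameter before concentrations are available, for example a missing 72 h sample for AUClast, or missing samples around the expected peak for Cmax. Align 9.3.1 and 11.1.1.2 with this rule. Report the complete-sample set as a single sensitivity analysis.

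The criteria should stay short. A missing Period 2 predose value need not void either parameter. Section 6.2.3 sets the interval "in order for the plasma concentration at Period 2 predose to be decreased below 5% of" the Period 1 peak, but this only justifies the washout; no predose exclusion check is stated. On the illustrative curve, taking a predose value at 5% of Cmax as zero changes AUClast by 0.05%. Likewise, consecutive losses at late times such as 36 and 48 h do not bear on Cmax when tmax is about 7 to 11 h.

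The cost is wording in three sections and one extra table. AUClast and Cmax become slightly less exact in a few subjects, and the two endpoints may have different subject numbers. If the lost sample is the observed peak, Cmax falls by a median 2.6% to 4.7% under an assumed 5% to 10% sample noise. For one such subject of 28 this moves the Cmax ratio by about 0.1% to 0.2% (2.6/28 to 4.7/28).
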